13.4. HRQL Questionnaires

13.4.1. EORTC QLQ-HN35

The EORTC QLQ-HN35 is a disease-specific module capturing HRQL dimensions that affect patients with head and neck cancer. It is composed of 7 symptom scales (pain, swallowing, senses, speech, social eating, social contact, sexuality), 6 symptom items (problems with teeth, trismus, xerostomia, sticky saliva, coughing, feeling ill), and 5 dummy (yes/no) items (use of painkillers, use of nutritional supplements, use of feeding tube, weight decrease, weight increase), for a total of 35 items. Participants' answers are collected with a one-week recall period. Symptom scales and items are presented in 4-point Likert scales.

Large international samples (N=662) exhibited a high internal reliability (Cronbach's $\alpha > 0.70$), construct validity (multi-trait scaling analysis $\rho \ge 0.40$) and criterion validity (as assessed by group comparison method) of the instrument (Bjordal et al. 2000; Sherman et al. 2000).

The EORTC QLQ-HN35 module has been validated for the different anatomical subsites, multiple disease stages, different treatment modalities (i.e., RT, chemotherapy, CRT and surgery) and across multiple countries (Bjordal et al. 1999; Bjordal et al. 2000; Singer et al. 2009). Validated translations of the EORTC QLQ-HN35 are available in 65 languages, including languages from European, Asian and Latin American countries covering target study sites. The instrument is meant to be used in conjunction with the EORTC core cancer module (EORTC QLQ-C30).

A specimen of the questionnaire (UK English) is available at https://qol.eortc.org/questionnaire/qlq-hn35/.

13.4.2. EORTC QLQ-C30

The EORTC QLQ-C30 version 3.0 questionnaire captures HRQL dimensions that are common to patients with cancer independently of the cancer type by which they are affected. It is composed of 5 functional scales (emotional, physical, cognitive, social and role), 3 multi-item scales (fatigue, pain, nausea/vomiting) and 6 single-item scales (dyspnea, insomnia, appetite loss, constipation, diarrhea, financial difficulties) and one global health scale, for a total of 30 items (Aaronson et al. 1993).

Participants' answers are collected with a one-week recall period and questionnaire items are presented in Likert scales (7-point scale for global health status, 4-point scale for all other items).

The internal reliability and construct validity of the instrument have been tested in large international samples of heterogeneous head and neck patients; validated translations of the EORTC QLQ-C30 are available for more than one hundred languages (Bjordal et al. 2000).

For both selected EORTC questionnaires, a score variation of at least 10 points for each item is considered clinically meaningful (King 1996; Osoba et al. 1998; Bjordal et al. 2000; Hammerlid et al. 2001; Cocks et al. 2011; Cocks et al. 2012). The 10-point threshold of clinical significance has been defined across different cancer indications and could be lower in specific cancer types (Cocks et al. 2011; Cocks et al. 2012).

A specimen of the questionnaire (US English) is available at https://qol.eortc.org/questionnaire/eortc-qlq-c30/.

13.5. Response Evaluation Criteria in Solid Tumors (RECIST) V1.1 Applied to this Study in Locally Advanced SCCHN

The text below was derived from Eisenhauer et al. 2009 and Schwartz et al. 2016. Guidance, adjustments and clarification specific to this study in locally advanced SCCHN, and not necessarily in the original articles, has been added.

Background and definitions

Response and progression will be evaluated in this study based on the international criteria proposed by the RECIST Working Group (Version 1.1). Unidimensional measurements of tumor lesions are used in the RECIST criteria. Individual lesions are either measurable or non-measurable using the criteria provided below.

Study-permitted imaging modalities and associated procedures

CT. MRI

CT is the best and most reproducible method currently available to measure lesions selected for response assessment. If CT scans have a slice thickness greater than 5 mm, the minimum size for a measurable lesion should be twice the slice thickness. MRI is also acceptable in this study, except for chest imaging, where CT is mandatory.

Ultrasound

Ultrasound is not useful in assessment of lesion size and should not be used as a method of measurement. Needle localization images for biopsy site may however be useful.

Endoscopy, laparoscopy

The utilization of these techniques alone for objective tumor evaluation is not permitted in this study. In this study, biopsy (endoscopic or otherwise) of a suspected new lesion to confirm or exclude malignant nature and provide relevant histological information is strongly encouraged when clinically feasible. Unbiopsied apparent recurrences visible only on endoscopy are not considered sufficient evidence alone to be markers of progression.

Tumor markers

Tumor markers for progression are not used in this study.

Cytology, histology

In this study, biopsy of a suspected new lesion or residual/recurrent mass to confirm or exclude malignant nature and provide histological information relevant to the endpoint is strongly encouraged when clinically feasible.

¹⁸F-FDG -PET + CT

This study incorporates 18F-FDG -PET scanning to complement CT/MRI scans in assessment of progression (particularly possible 'new' disease.) However, the use of 18F-FDG-PET to upgrade response to CR unsupported by biopsy is not applied to this study.

Assessment methodology

• Assessment methodology of measurable lesions selected for measurement

Non-nodal tumor lesions must be accurately measured in one dimension, the longest diameter in the plane of measurement, with a minimum size of 10 mm by CT scan (irrespective of scanner type) and MRI (no less than double the slice thickness and a minimum of 10 mm.) Clinical observations, clinical caliper measurements, photographic assessments, and plain radiographs are not permitted in this study. All measurements should be recorded in metric notation.

The short axis of a lymph node, or conjoined mass of nodes, is the longest perpendicular to the longest diameter in the axial plane. To be considered pathologically enlarged and measurable at baseline, a lymph node must be ≥ 15 mm in short axis when assessed by CT or MRI scan (Scan slice thickness recommended to be no greater than 5 mm). At baseline and in follow-up, only the short axis of nodes will be measured and followed.

Assessment methodology of non-measurable disease

All other lesions (or sites of disease), including small lesions (< 10 mm using spiral CT or MRI scan), as well as measurable lesions that are not selected as target lesions, are considered non-measurable disease. RECIST criteria define many baseline types of lesion that are always non-measurable, but all of these are excluded from this study. Participants with only non-measurable disease at baseline but whose overall disease burden is still assessable by imaging are considered to have evaluable (non-measurable) disease.

- Assessment of special lesion types
 - a) Bone lesions. There will be no malignant bone lesions at baseline in this study due to inclusion/exclusion criteria, hence discussion of measurability of bone lesions at baseline and of lesions seen at baseline on bone scans is unnecessary.
 - b) Cystic lesions. Radiographically defined simple cysts should not be considered as malignant lesions. Complex malignant cystic lesions will not occur at baseline in this study due to inclusion/exclusion criteria and hence need not be considered further
 - c) Lesions with local irradiation: In this study, all lesions seen at baseline will receive irradiation as part of the study treatment, and therefore it is impossible to avoid radiation impact on assessments. As a result, the processes of selection and following of target lesions should not be influenced by past or current irradiation.

Process for evaluation of disease at baseline

All baseline evaluations should be performed as close as possible to the treatment start and never more than 4 weeks before the beginning of the treatment. The same method of assessment and the same technique should be used to characterize each identified and reported lesion at baseline and during follow-up.

Target Lesions

All measurable lesions up to a maximum of 2 lesions per organ and 5 lesions in total, should be identified as **target lesions** and recorded and measured at baseline. Target lesions should be selected on the basis of their size (lesions with the longest diameter), be representative of all involved organs, but also should be those suitable for reproducible repeated measurements.

Lymph nodes: Pathological nodes which are defined as measurable and may be identified as target lesions at baseline must have a short axis of \geq 15 mm by CT or MRI scan. Only the short axis of these nodes will contribute to the baseline sum of diameters. All other pathological nodes (those with short axis \geq 10 mm but < 15 mm) should be considered non-target lesions. Nodes that have a short axis < 10 mm at baseline are considered non-pathological and should not be recorded or followed.

A sum of diameters (longest for non-nodal lesions, short axis for nodal lesions) for all target lesions will be calculated and recorded as the **baseline sum of diameters**. The baseline sum of diameters will be used as reference to further characterize any later objective tumor changes in the measurable dimension of the disease.

• Non-target Lesions

All other lesions (or sites of disease) including pathological lymph nodes should be identified as **non-target lesions** and should also be recorded at baseline. Measurements are not required, except short axis of nodes and then only to confirm or exclude pathological enlargement: these lesions should be followed as 'present', 'absent', or reported overall as 'unequivocal progression'. Multiple non-target lesions involving the same organ can be a single item on the case record form (e.g., 'multiple liver metastases').

Process for assessment of disease at each timepoint after baseline

• Evaluation of Target Lesions

A new sum of diameters for all target lesions will be calculated and recorded as the **sum of diameters** for that timepoint. This timepoint sum of diameters will be used for comparison with that at baseline and at the timepoint when the sum of diameters is least (the nadir): the details of the outcome of each comparison are shown in Table 1 below.

Table 1 Response Status Definition for Target Lesions at each Timepoint

Observed disease	Response	Abbreviation
Disappearance of all target lesions except pathological lymph nodes. Any pathological nodes (target or non-target) must have reduction in short axis to < 10 mm.	Complete Response	CR
At least a 30% decrease in the sum of diameters of target lesions, taking as reference the baseline sum of diameters.	Partial Response	PR
At least a 20% increase in the sum of diameters of target lesions, taking as reference the smallest sum on study or at baseline (the nadir.) In addition to the relative increase of 20%, the sum must also demonstrate an absolute increase of at least 5 mm.	Progressive Disease	PD
Neither sufficient shrinkage to qualify for PR nor sufficient increase to qualify for PD, taking as reference the smallest sum of diameters at baseline or on study.	Stable Disease	SD
One or more target lesions have not been assessed or assessed using a different modality from baseline or nadir, so adequate comparison of the images is impossible.	Not Evaluable	NE

Special points

Lymph nodes. Lymph nodes identified as target lesions should always have the actual short axis measurement recorded even if the nodes regress to below 10 mm on study. This means that, when lymph nodes are included as target lesions, the sum of diameters may not be zero even if CR criteria are met. In order to qualify for CR, each node must achieve a short axis < 10 mm. For PR, SD, and PD, the actual short axis measurement of the nodes also is to be included in the sum of diameters of target lesions.

Target lesions that become 'too small to measure'. While on study, all lesions (nodal and non-nodal) recorded at baseline should have their actual measurements recorded at each subsequent evaluation, even when very small. However, sometimes the radiologist may not feel able to assign an exact measure and may consider them 'too small to measure'. If it is the opinion of the radiologist that the lesion has likely disappeared, the measurement should be recorded as 0 mm. If the lesion is believed to be present and is faintly seen but too small to measure, a default value of 5 mm should be assigned.

Lesions that split or coalesce on treatment. When non-nodal lesions 'fragment', the longest diameters of the fragmented portions should be added together to calculate the target lesion sum. Similarly, as lesions coalesce, a plane between them may be maintained that would aid in obtaining maximal diameter measurements of each individual lesion. If the lesions have truly coalesced such that they are no longer separable, the vector of the longest diameter in this instance should be the maximal longest diameter for the 'coalesced lesion'.

Target lesions that are biopsied or excised: On occasion, target lesions may be biopsied or excised. Measurements of such lesions may no longer be suitable for accurate assessment of response and/or progression. In this situation a sum of diameters including any residual lesion should still be calculated, and if the sum of diameters is still increased by 20% over nadir, disease progression is diagnosed. If doubt remains, the entire disease burden of the participant should be considered and compared with that at baseline as though there was only evaluable, non-measurable disease at baseline. In such a situation, non-CR/non-PD becomes a possible timepoint assessment and even best overall response even though there was measurable disease at baseline. To minimize the risk of this eventuality, study imaging before biopsy is advised.

Evaluation of Non-target Lesions

While some non-target lesions may actually be measurable, they need not be measured (except lymph nodes when pathological nature is uncertain) and instead should be assessed only qualitatively, according to the timepoint assessment criteria shown in Table 2 below:

Table 2 Response Status Definition for Non-target Lesions at each Timepoint

Observed disease	Response	Abbreviation
Disappearance of all non-target lesions except for lymph nodes. All lymph nodes must be non-pathological in size (< 10 mm short axis).	Complete Response	CR
Persistence of one or more non-target Lesions.	Neither complete response nor progressive disease	Non-CR/non-PD
Unequivocal progression of existing non-target lesions	Progressive disease	PD

Observed disease	Response	Abbreviation
No non-target lesions seen at baseline	No non-target lesions	NA
Assessment not possible due to inadequate or missing images.	Not Evaluable	NE

Special points

When the participant has both target and non-target lesions. To achieve 'unequivocal progression' on the basis of the non-target disease, there must be an overall substantial worsening in non-target disease such that, even in the presence of SD or PR in target disease, the overall tumor burden has increased sufficiently to merit new therapy. A modest 'increase' in the size of 1 or more non-target lesions is insufficient to quality for unequivocal progression status. The designation of overall progression solely on the basis of change in non-target disease in the face of SD or PR of target disease will therefore be extremely rare.

When the participant has only non-target lesions. In this study, it is not a requirement for study entry to have measurable disease. The same general concepts apply here as noted above; however, in this instance there will be no measured disease assessment to balance the interpretation of an increase in non-measurable disease burden. The test that should be applied when assessing participants for unequivocal progression is to consider if the increase in overall disease burden based on the change in non-measurable disease is at least comparable in magnitude to the increase that would be required to declare PD for measurable disease.

Evaluation of New Lesions

The appearance of new malignant lesions denotes disease progression by RECIST v1.1. The finding of a new lesion should be unequivocal: i.e., not attributable to differences in scanning technique, change in imaging modality, or findings thought to represent something other than tumor. A lesion identified on a follow-up study in an anatomical location that was not scanned at baseline is considered a new lesion and will indicate PD. Exceptionally, since the endpoints of this study differentiate between locoregional progression and distant metastasis, it is necessary to differentiate between locoregional lesions and metastases elsewhere. Therefore, data on new lesions in each of these *locations* will be required if available. If the first manifestation of disease progression is distant metastasis, then assessments for locoregional control should continue if possible, and vice versa. Note: As this study is in locally advanced disease, all target and nontarget lesions at baseline will lie within the locoregional volume and therefore no similar differentiation at baseline is possible or required.

If a new lesion is equivocal, either continued therapy and follow-up evaluation or biopsy and histological examination will clarify if it represents truly new disease. If repeat scans or biopsy confirm a new lesion, then PD should be declared using the date of the initial scan.

In case histopathological results of a new lesion unequivocally reveal a non-squamous histology of the new malignant lesion, this will not be counted as disease progression within the primary or secondary endpoints of this study.

Evaluation of disease status at each post-baseline timepoint

For participants with measurable disease, the assessment of response status at each timepoint will be an *amalgamation* of the individual response statuses of target lesions, non-target lesions and new lesions, and is shown in Table 3 below.

Table 3 Timepoint Assessment of Disease Status by Imaging for Participants with Measurable Disease at Baseline.

	Timepoint response in:			
Target Lesions	Non-Target Lesions	New Lesions	Overall Timepoint Response	
CR	CR	No	CR	
CR	Non-CR/non-PD	No	PR	
CR	NE	No	PR	
PR	Any, except PD or NE	No	PR	
SD	Any, except PD or NE	No	SD	
Not all measured	Any, except PD	No	NE	
PD	Any	Yes or no	PD	
Any	PD	Yes or no	PD	
Any	Any	Yes	PD	

CR=complete response, NE=not evaluable, PD=progressive disease, PR=partial response, SD=stable disease.

The RECIST papers referenced in this document provide no similar assessment paradigm for response status at timepoint for participants with evaluable but non-measurable disease at baseline, but one can be derived from the information above, and it is provided in Table 4 below.

Table 4 Timepoint Assessment of Disease Status by Imaging for Participants with Nonmeasurable Disease at Baseline, or due to Biopsy or Excision

Timepoint response		Overell Timeneint Beenenee	
Non-Target Lesions	New lesions	Overall Timepoint Response	
CR	No	CR	
Non-CR/non-PD	No	Non-CR/non-PD	
NE	No	NE	
PD	Yes or no	PD	
Any	Yes	PD	

CR=complete response, NE=not evaluable, PD=progressive disease.

Special points

Impact of biopsy and excision. Due to biopsy or excision of target lesions, some participants with measurable *disease* at baseline may have a timepoint response or best overall response of Non-CR/Non-PD

Symptomatic progression. Symptomatic progression alone is not a determinant of disease progression in this *study.*

Handling equivocal findings of progression. For equivocal findings of progression (e.g., very small and uncertain new lesions; cystic changes or necrosis in existing lesions), in the absence of histological verification of new malignant lesions, treatment may continue at the investigator's discretion until the next scheduled assessment. If, at the next scheduled assessment, progression is definite, the date of progression should be the earlier date when progression was first suspected

Further information

Further information on the assessment of disease by imaging in this study is available in the training materials, including slide presentations and videos.

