9.12.3 Tumor Evaluation and Adjudication

Missing data from scheduled Tumor assessments not performed will not be imputed. Evaluable Tumor assessments are defined as those with overall response CR, PR, SD or PD for patients with measurable disease or CR, Non-CR/non-PD, or PD for patients with non-measurable disease only at baseline. Data from non-evaluable (NE) Tumor assessments will be used in the derivation of endpoints in accordance with Eisenhauer et al., (2009).

In case BIRC assessments are performed only the response assessments which are flagged as accepted after adjudication will be taken over to ADaM datasets and will be analyzed. In case of a missing adjudication flag for a response assessment and earliest image dates are equal, the assessment of reader 1 (the reader who completed baseline first) will be taken for analysis. Otherwise, the assessment for the reviewer who reviewed the record with the earliest image date will be analyzed. Analyses of tumor sizes will be based only on assessments of the reader whose assessment was accepted at baseline.

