14.1 Primary Efficacy Endpoint: Event-free Survival (EFS)

Event-Free Survival (EFS) time is defined as the time (in months) from randomization to the first occurrence of any of the following events as assessed by the BIRC: death due to any cause, disease progression (radiological or clinical), primary treatment failure, relapse (radiological or clinical) or occurrence of a new cancer (see Table 1). Death as reported on the eCRF page "Death" will also be considered in the derivation of EFS time.

$$EFS = (date of EFS event - randomization date +1) / 30.4375$$

Censoring rules for the primary and sensitivity analyses of EFS are described in Table 4 below. The last adequate tumor assessment is defined as the last tumor assessment result that is not "Not evaluable" or "Not assessed". If a participant is meeting a multiple censoring situation, the earliest censoring criterion will be applied.

Table 4: Censoring rules for EFS

Situation	Primary	Sensitivity #1	Sensitivity #2
No evaluable baseline or post-baseline assessment*	Right censored at the date of randomization	Right censored at the date of randomization	Right censored at the date of randomization
Death, PD or any event entering in the definition of EFS after 2 or more consecutive missing or inadequate tumor assessments	Right censored at last adequate assessment before the consecutive missing/inadequate assessments	Right censored at last adequate assessment before the consecutive missing/inadequate assessments	Not applicable
Initiation of a new anticancer treatment for the disease under investigation before any event entering in the definition of EFS	Right censored at their last adequate assessment before the initiation of the new anticancer treatment	Not applicable	Not applicable
No death, PD, nor any event entering in the definition of EFS	Right censored at the date of their last adequate assessment	Right censored at the date of their last adequate assessment	Right censored at the date of their last adequate assessment

Abbreviations: EFS: Event-free survival; PD: Progressive disease

^{*}Any EFS event is considered as a post-baseline assessment.

Table 5: Estimand Attributes EFS

Objective	Estimand Attributes
Primary	

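### Table 3 of protocol Appendix 13.5 accepts unreadable non-target disease with target CR but not with target PR or SD, and leaves three combinations without an overall response

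*Protocol*

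**What the plan says.** Appendix 13.5 of the protocol gives the response rules, and Section 8.2 applies them to both local and central assessment. Table 2 of the appendix defines the non-target codes. NA is used where there were "No non-target lesions seen at baseline", and NE means "Assessment not possible due to inadequate or missing images".

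Table 3 then assigns the overall response for participants with measurable disease. Target CR has three rows without a new lesion: non-target CR gives CR, non-CR/non-PD gives PR, and NE gives PR. Target PR and target SD have one row each, and both restrict non-target status to "Any, except PD or NE". The only row that produces an overall NE reads "Not all measured Any, except PD No NE", so it applies when target lesions were missed.

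SAP Section 9.12.3 states: "Evaluable Tumor assessments are defined as those with overall response CR, PR, SD or PD for patients with measurable disease". SAP Section 14.1 defines an adequate assessment separately, as any result other than the codes for not evaluable or not assessed. Under the primary rule in SAP Table 4, an EFS event after two or more consecutive missing or inadequate assessments is "Right censored at last adequate assessment before the consecutive missing/inadequate assessments". Participants without an event are censored at their last adequate assessment. Those who start a new anticancer treatment before any event are censored at the last adequate assessment before that start. The primary estimand in SAP Table 5 counts events that fall within two scheduled assessments of the last evaluable one.

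**The concern.** The same missing information is tolerated for the strongest target result and barred for the weaker ones. If target CR with unreadable non-target disease can be called PR, it is hard to see why a measured target PR or SD with the same gap should have no answer. The appendix gives no reason.

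The gap matters because the overall timepoint response decides whether a scan is evaluable. That status enters the EFS estimand, the EFS and PFS censoring rules and best overall response. Where the table is silent, the blinded independent review committee (BIRC) and the investigators may fill the gap differently, which adds avoidable discordance between the primary analysis and its investigator-based sensitivity analysis.

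The missing CR+NA row is a separate matter. CR status feeds the complete response rate and time to CR. It also decides which EFS branch applies: radical salvage surgery needs documented viable tumor before a CR, but counts whatever the pathology shows after one.

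**Working it through.** **Step 1: completeness of Table 3.** The inputs are the non-target codes of Table 2 and the rows of Table 3, both in Appendix 13.5. For fully measured, non-progressing targets, no new lesion and no non-target PD, the outcomes are:

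| Target | Non-target CR | Non-CR/non-PD | NE | NA |
|---|---|---|---|---|
| CR | CR | PR | PR | no row |
| PR | PR | PR | no row | PR |
| SD | SD | SD | no row | SD |

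Three of these 3 × 4 = 12 cells are empty. Over all 5 target codes (CR, PR, SD, PD, NE) and 5 non-target codes (the four above and PD), the count is 3 of 25. The row giving an overall NE does not fill the PR+NE or SD+NE cells, because it concerns unmeasured targets.

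**Step 2: what follows in the SAP for PR+NE and SD+NE.**
- Section 9.12.3: with none of CR, PR, SD or PD assigned, the scan is not evaluable.
- Section 14.1: whether it is also inadequate depends on how it is recorded. NE or not assessed makes it inadequate; a blank is not addressed.
- Section 9.15: best overall response needs at least one recorded PR or SD, so the scan cannot supply it.
- SAP Table 4, no event: the censoring date moves only if the affected scan is the last one. The shift is then one visit interval, which in protocol Table 1-3 is 3 months between Months 9 and 36 and 6 months afterwards. The same holds for the last scan before a new anticancer treatment.
- SAP Table 4, event: two or more consecutive affected or missing scans must immediately precede the event. An adequate scan in between resets the count.

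**Step 3: size.** The documents give no rate of non-target NE and no figure on this point, so the rate is an assumption. As a base, the EFS design figures in SAP Section 6 were reproduced. The inputs were looks at 279, 365 and 429 events, 0.025 one-sided, Lan-DeMets O'Brien-Fleming-type spending, HR 0.73, 1:1 allocation, and stopping at the futility HR of 0.886 at the first look.
- Boundary p-values are 0.0054, 0.0135 and 0.0202 (stated 0.005, 0.013 and 0.020).
- Boundary HRs are 0.737, 0.793 and 0.820 (stated 0.737, 0.793 and 0.821).
- Stagewise power is 53.3%, 25.8% and 9.1%, in total 88.2%, as stated.

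Let q be the NE rate per visit, independent across visits. The chance that both visits before an event are affected is q², so the expected number of affected events is 429 × q²:
- q = 2%: 429 × 0.0004 = 0.2
- q = 5%: 429 × 0.0025 = 1.1
- q = 10%: 429 × 0.01 = 4.3

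NE that persists within a participant would raise these numbers.

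If those events were lost without replacement, fixed-design power is Φ(|ln 0.73| × √D / 2 − 1.96). With D = 429 this is 90.3%. With 1% lost (D = 424.7) it is 90.0%, and with 5% lost (D = 407.5) it is 88.8%. The analysis waits for its events, so delay and informative censoring are more likely than loss of power.

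**The case against.** The strongest reply is that this is a drafting gap whose consequences are conjectural. Much of that stands.

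- A reader might infer that Table 3 turns these scans into NE. It does not; it is silent. The fallback to NE for all other cases in SAP Section 9.15 is for best overall response, not for a timepoint. The training materials mentioned at the end of Appendix 13.5, or a BIRC charter, may settle the coding, but neither is among the documents.
- A reader might infer that a participant with target lesions only can never be a complete responder, or that a CR+NA scan is inadequate. Neither is supported. Overall response combines the component statuses, and with no non-target lesions there is nothing to combine, so target CR would probably be read as CR.
- A reader might infer that every affected scan moves a censoring date, or that any two in a row cost a later event. Step 2 shows that an adequate scan afterwards undoes both.
- Appendix 13.5 places all baseline lesions in the locoregional volume, so target and non-target disease normally share the head and neck scan. Measured targets with unreadable non-targets should be uncommon.
- There are buffers. The Sensitivity #2 censoring rule drops the missed-assessment condition, CRR and ORR are outside confirmatory testing, and the BIRC also reviews clinical and pathological data.

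What does not stand is the suggestion that nothing is wrong. The PR and SD rows exclude NE expressly, while a neighboring row accepts it. The appendix declares that "Guidance, adjustments and clarification specific to this study in locally advanced SCCHN, and not necessarily in the original articles, has been added", but that general notice does not explain the difference. Sensitivity #2 does nothing for response assignment.

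**Conclusion.** Table 3 is incomplete and internally inconsistent. PR+NE and SD+NE have no overall response despite fully measured targets, and under SAP Section 9.12.3 such scans are not evaluable unless someone assigns a response the table does not give. The harm to EFS depends on the gap being left blank or coded NE, and on the scan being the last one or part of a run of two or more immediately before an event.

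The likely size is small: about 0.2 to 4.3 of 429 events if NE arises independently at 2% to 10% per visit, and more if it clusters within participants. That rate is assumed. The CR+NA gap bears on CR assignment only. Its size cannot be stated, because the documents do not say how many participants have target lesions only. The point merits correction because it is cheap to remove and touches the primary endpoint, not because it threatens the trial's conclusion.

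**What to change.** In Table 3 of Appendix 13.5, let the target PR and SD rows accept every non-target status except PD, so that NE is admitted. Change the first row so that target CR with non-target CR or NA and no new lesion gives CR. Apply this to both BIRC and investigator timepoint derivation before unblinding. Timepoints already recorded need re-derivation from the stored target, non-target and new-lesion codes, not a new reading of the images.

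The cost is three table cells, the matching derivation programs and some re-derivation work. A few PR and SD calls would rest on target lesions alone, which the table already allows for target CR with NE.
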